3.2 Post-Discharge Psychotherapeutic Recovery Support Program

For application to patients at high risk of early readmission who meet the inclusion criteria. The proposed psychotherapeutic intervention is considered as an adjunct to the standard treatment received by patients, as well as to the intensive case management measures proposed. It consists of a multicomponent group psychotherapeutic intervention from a rehabilitative and recovery-oriented perspective (10) This intervention will be structured into 20 sessions, each lasting 90 minutes, held weekly in an open format. It will be directed by two cotherapy professionals. The group will consist of a maximum of 12 participants, who may join at different times.

The intervention program includes different areas of work that are developed in a transversal way throughout the 20 sessions, following an open and flexible semi-structured format. Each area of work was included based on the available evidence regarding the effectiveness of psychosocial and psychotherapeutic interventions collected in scientific literature, Clinical Practice Guidelines, and the Integrated Care Process in Severe Mental Disorder of the Andalusian Health Service (8–12). The contents addressed by the Post-discharge Recovery Support Psychotherapeutic Program can be grouped around the following areas:

- Initial Phase: Introduction. Explanation of the framework and group rules. Addressing group objectives. Exploring personal expectations and identifying needs. Initiating therapeutic rapport and fostering group cohesion. These aspects will be addressed throughout the intervention and will be more evident during the welcoming of new group participants.
- Interpersonal Management: With the aim of promoting interpersonal functioning and independence, as well as adaptation to the community, dysfunctional relationship patterns will be addressed, which will be manifested in the group's own functioning. Both social perception skills or reception, social cognition or processing skills, and behavioral response or expression skills will be addressed.
- Problem Solving: This area of work aims to establish a link between symptoms and practical difficulties in their immediate context. Identifying and breaking down the problem, setting achievable goals, generating solutions, implementing them, and evaluating the results will be some of the skills to work on.

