The experimental group, to which the Discharge Transition Intervention Program will be applied, will consist of users whose Community Mental Health Units (CMHU) are affiliated with the Regional Hospital of Málaga. Users belonging to other hospitals in the province will be excluded from the intervention program and will form part of the control group.

Participants included in the Post-Discharge Group Psychotherapy Support Recovery Program will be those at high risk or with an early rehospitalization already occurred, who also meet the inclusion criteria. The relevance of their inclusion will be assessed through a clinical interview by the Specialist in Clinical Psychology in charge of the program, following these criteria.

Inclusion criteria:

- Be of legal age.
- Speak spanish fluently.
- Have had recent admission to the MHHU of the Regional Hospital of Málaga and a score considered as "High Risk" on the Early Rehospitalization Risk Scale or have experienced an early rehospitalization.
- Belong to the Clinical Management Unit of Mental Health of the RUH of Málaga.
- Have sufficient cognitive capacity to understand the rules and contents of the group intervention.

Exclusion criteria:

- Individuals whose primary diagnosis is a Mental and Behavioral Disorder due to psychoactive substance use.
- Moderate or severe intellectual disability.
- Clinical Management Unit belonging to a hospital other than the RUH of Málaga.
- Lack of commitment to attending sessions or complying with group rules.

- **Study variables**

Main outcome variables

The main outcome variable will be the risk of early reentry of the experimental group compared to the control group, which did not follow the intervention.

Secondary outcome variables

The risk of early rehospitalization of the admission episodes from the experimental group will be compared to the risk of early rehospitalization of admission episodes from the previous year.

Frequent rehospitalization will be assessed as having undergone at least two readmissions within a 6-month follow-up period. The risk of frequent rehospitalization will be considered as a secondary variable.

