In order to assess the effectiveness of the Recovery Support Psychotherapeutic Program, pre- and post-intervention scales will be administered to all participants to take into account other psychological and clinical variables. This evaluation will be conducted by blinded evaluators before the program begins and upon its completion, after the last session. The instruments to be used are as follows:

-Core Om (13,14): It is a self-report questionnaire composed of 34 items that allows for a brief assessment of the patient's status, widely used for evaluating therapeutic change based on four dimensions: Subjective well-being, Problems/Symptoms, General functioning, and Risk scale. The questionnaire items are scored on a Likert scale from 0-4. It is a valid and reliable instrument in its Spanish version.

- The Duke Social Support Questionnaire (Duke-unk-11) (15,16), assesses the perceived degree of social support. It is a self-administered questionnaire consisting of 11 items and a Likert-type response scale (1-5).

- The Personal and Social Performance Scale (PSP) (17,18), It is a hetero-applied and very brief instrument that allows quantifying changes in the functional recovery of patients in the following areas: a) self-care; b) usual social activities, including work and study; c) personal and social relationships; and d) disturbing and aggressive behaviors. The result on the scale is established by assigning to each of the areas a severity level. The total score ranges from 0 to 100.

- Recovery Process Questionnaire (QPR-15-SP) (19) is a self-reported questionnaire used to assess progress in measures of recovery linked to overall psychological well-being, personal achievements, quality of life, and empowerment. It consists of 15 items on a Likert scale from 0 to 4, with a high score indicating recovery. It has adequate reliability and validity indices and has been psychometrically adapted and validated in the Spanish population (20).
- Client's Assessment of Treatment (CAT). This scale evaluates patient satisfaction with hospital treatment, and in this study, it will be adapted to extend this measure to the overall mental health treatment received. Users rate each item on a scale from 0 to 10 (21,22).

- **Data analysis**

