In the analysis for the creation of the early rehospitalization risk scale, a univariate logistic regression analysis will be used. For the final selection of factors, a forward stepwise multivariate analysis will be performed, introducing variables with greater statistical significance. Finally, a scale will be developed to measure the risk of early rehospitalization in each admission episode, whose sensitivity and specificity will be tested beforehand using a receiver operating characteristic (ROC) curve. The construction of the scale will follow the procedure outlined in detail in Sullivan et al. (23).

To evaluate the differences between the intervention group and the control groups, a univariate and multivariate mixed logistic regression analysis will be conducted, introducing potential confounding variables (unit occupancy, age, sex, and the variables used in the scale for estimating the risk of early rehospitalization). To assess potential differences in Core Om, Duke-unk-11, PSP, and QPR among patients participating in the Post-Discharge Recovery Support Psychotherapy Program, the paired Student's t-test for repeated measures or the non-parametric Wilcoxon signed-rank test for a single sample will be used.

DISCUSSION

The present research study aims to analyze the risk factors for early rehospitalization of patients discharged from a short-term psychiatric hospitalization unit. Based on this information, the goal is to stratify the risk and direct more intensive therapeutic measures to those individuals with a higher likelihood of rehospitalization to reduce early rehospitalization rates.

Thus, determining the risk of psychiatric rehospitalization for individual patients is a critical step in efforts to address the potentially avoidable high rate of this negative outcome, as highlighted in the READMIT study (4). This study conducted in Canada succeeded in providing a framework to identify patients at high risk of rehospitalization through the development of a prognostic index with moderate discriminative capacity.

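### Therapy-group participants who leave early have no defined post-score, so the paired tests cover completers only and will probably overstate improvement if leavers do worse

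*Combined protocol and SAP*

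**What the plan says.** The combined protocol and SAP deals with the therapy group in four places.

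- **Section 3.2 (Post-Discharge Psychotherapeutic Recovery Support Program):** "This intervention will be structured into 20 sessions", held weekly with rolling entry and at most 12 members at a time. A full course therefore lasts about 20 weeks from each person's first session.
- **Study variables, Secondary outcome variables:** "pre- and post-intervention scales will be administered to all participants", and the assessments take place "before the program begins and upon its completion, after the last session". No interim assessment, and none at withdrawal, is described.
- **Data analysis:** for Core Om, Duke, PSP and QPR "the paired Student's t-test for repeated measures or the non-parametric Wilcoxon signed-rank test for a single sample will be used". The group analysed is described only as those "among patients participating in the Post-Discharge Recovery Support Psychotherapy Program". The CAT is administered, but this sentence names no test for it.
- **Participants and recruitment:** "The relevance of their inclusion will be assessed through a clinical interview". One of the exclusion criteria is "Lack of commitment to attending sessions or complying with group rules".

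The document does not define an analysis set or a minimum number of sessions, and does not say how a missing post-score is handled.

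**The concern.** The only post-assessment is tied to finishing the programme. A person who stops attending after a few weeks, or whose course is cut short by a readmission, has no date on which the second score is due. A paired test cannot use a single score, so that person disappears from the result.

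The evaluation is single-arm, before against after. In a two-arm comparison, similar loss in both arms might partly cancel; here nothing offsets it. The stated aim refers to patients at high risk of early readmission, but the analysis would answer for those who stay.

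The document gives reasons to expect loss. Entrants are at high risk or have already been readmitted. The Discussion expects difficulties with group work. The case manager's duty to re-engage non-attenders covers only the first month after discharge, and the programme lasts about five. Post-scores that are not collected from leavers cannot be recovered afterwards.

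**Working it through.** The plan states no sample size, drop-out rate, SD or effect size for the therapy group, so there is no figure to reproduce. The sums below show how large the bias could be under stated assumptions.

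**1. What the text implies.** The post time point is programme completion, at about 20 weeks. The test needs both scores. A leaver who is not assessed at another time therefore contributes nothing.

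**2. Bias in the completers' mean.** Assumptions:
- change is standardised to SD 1, with positive meaning improvement, and its true mean is 0;
- staying is driven by a normal latent variable with correlation ρ to the patient's own change;
- a fraction d has no post-score.

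The completers' mean change is ρ × φ(z_d) / (1 − d), where z_d is the d-quantile of the standard normal and φ its density.

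| d | φ(z_d) | φ(z_d)/(1 − d) | ρ = 0.3 | ρ = 0.5 |
|---|---|---|---|---|
| 20% | 0.280 | 0.350 | 0.105 | 0.175 |
| 30% | 0.348 | 0.497 | 0.149 | 0.248 |
| 40% | 0.386 | 0.644 | 0.193 | 0.322 |

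The spurious gain is about 0.10 to 0.32 SD of change. With ρ = 0 it is 0. With ρ = −0.3 it is −0.105 to −0.193 SD over the same range of loss, so improvement would be understated.

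**3. False-positive rate.** Assume one group with every place filled for 12 months: 12 × 52 / 20 = 31.2, so about 31 entrants. This is a capacity figure, not a planned sample size. In 20,000 simulated paired t-tests per setting, with true change zero, the chance of a significant improvement (nominal 2.5% in that direction) was:

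| d | ρ = 0 | ρ = 0.3 | ρ = 0.5 |
|---|---|---|---|
| 20% | 2.4% | 7.7% | 14.2% |
| 30% | 2.4% | 9.7% | 21.2% |
| 40% | 2.5% | 12.5% | 29.1% |

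**4. Would a mixed model be enough?** Take equal variances before and after, pre–post correlation r (assumed), and drop-out that depends on the patient's own change as in step 2. Let k = φ(z_d)/(1 − d) and s = √((1 − r)/2). Among completers the pre-score mean shifts by −kρs and the post-score mean by +kρs, so the bias in change is 2kρs. A likelihood analysis that keeps pre-only participants corrects the post mean by regression on the pre-score, with slope about r. The bias left is kρs(1 + r). The fraction remaining is therefore about (1 + r)/2: 0.65 at r = 0.3 and 0.85 at r = 0.7. Simulation gives 66–87%. The model removes only a minor part of this bias, and collecting the missing scores is what matters.

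**The case against.** The strongest reply is that the plan nowhere specifies a completers-only analysis. It says that the scales go to all participants, and the analysis sentence refers to those taking part, not those who finish. The last session could be read as each person's own last one. This stands in part: the intention to assess everyone is there. But the sentence ties the second assessment to completion of the programme and gives no date or procedure for someone who simply stops coming.

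A second reply is that the direction of bias is not established. This stands. The document gives no drop-out rate and no reasons for leaving.

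Three stronger readings are tempting, and the document does not support them.

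- *The commitment exclusion strips out non-attenders after entry.* The criteria are placed at an inclusion interview, where willingness to attend can be judged. Used there, the criterion narrows who the result applies to but does not bias the change among entrants. The text does not say that it is applied later, although it does not rule it out.
- *All five scales are affected.* The paired tests are named for four.
- *The false-positive rate is 19–37% per scale.* Shifts of 0.2 and 0.3 SD with 31 completers do give 19% and 37%. But 31 is the assumed number of entrants, and with 20–40% loss about 25 to 19 would complete. Counting 31 entrants gives the 8–29% in the working.

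**Conclusion.** The point holds as a weakness in a secondary analysis. Followed as written, the plan leaves early leavers without a post-score and drops them from a single-arm estimate. Overstated improvement on the four tested scales is likely if those who relapse, are readmitted or disengage are the ones lost. That is plausible in this population but not shown by the document.

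The size, 0.10–0.32 SD, rests wholly on assumed values: 20–40% loss, a retention–change correlation of 0.3–0.5 and a true change of zero. It should be read as an indication of scale, not a forecast. A reader might infer that the trial's main result is compromised. It is not, because the readmission comparison uses all admission episodes and does not depend on these scores.

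**What to change.** - Take the post-assessment at a fixed 20 weeks from each participant's own first session, whether or not they still attend. This is the essential change.
- Define the analysis set as everyone with a pre-score who attended at least one session.
- Analyse it with a repeated-measures mixed model that keeps participants with only a pre-score. Because the model alone does not remove the bias, add a missing-not-at-random sensitivity analysis, for example by assigning leavers a range of worse changes and reporting where the conclusion alters.
- Report the number and baseline scores of those without a post-score.
- Keep the paired test on completers as a sensitivity analysis, labelled as such.
- State that the commitment criterion defines the analysed group only at the entry interview, so that nobody is removed from the analysis after entry. This concerns who is analysed, not who continues in the group.

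The cost is a change of wording and some effort by the existing evaluators. On the assumed 31 entrants, 20–40% loss means about 6 to 12 people to reach in a year (0.2 × 31 = 6.2; 0.4 × 31 = 12.4). Most of the instruments are completed by the patient, and the document describes the PSP as very brief. The estimate may turn out less favourable.

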for analysis in the reference population: Sociodemographic factors (sex, age, marital status, legal incapacity, employment status, criminal history, and social functioning), psychiatric history (previous admissions, emergency service visits in the twelve months prior to admission, history of suicide attempts, attendance at community nursing follow-ups in the six months prior to admission, and somatic comorbidity), reasons for admission (presence of hetero- or auto-aggression or deficits in self-care), clinical characteristics (primary diagnosis, substance use, non-adherence to follow-up in the previous 12 months, and non-adherence to treatment up to one month before admission), admission characteristics (urgent or scheduled access route and length of stay), and discharge measures (coordination with referring physician in the CMHU and prescription of depot medication).

During admission to the hospitalization unit, all users must have the aforementioned Early Readmission Risk Scale of the MHHU of the RUH of Malaga administered. This will allow for the classification of patients according to their risk level, establishing defined cutoff points, resulting in three categories: Patients at low risk, medium risk, and high risk. This scale will be completed by the referring physician during the initial assessment interview upon admission to implement the proposed measures for each risk level. Additionally, the referring physician will establish contact with the case management figure responsible for the program for the referral of cases with a score indicative of a high risk of early readmission or patients with early readmission within 30 days post-discharge.

Intervention measures based on the risk of early readmission

For patients classified in the low-risk group, general measures would be applied. For patients in the medium-risk group, reinforced measures would be implemented. Lastly, for patients considered to be in the high-risk group, intensive case management measures would be applied, and if they meet the inclusion criteria, they would be included in the Post-Discharge Group Psychotherapeutic Intervention.

1. General measures

The following measures would be applied to patients with a low risk of readmission:

-Ensure coordination between physicians during admission and a follow-up appointment within 7 days.

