-If the patient presents substance abuse, ensure an appointment at the Provincial Drug Dependency Center (PDC) upon discharge and record the date in the discharge report.

-If the patient presents social impairment, refer them to a Social Worker at the MHHU during admission and initiate a social history.

2. Reinforced measures

The following measures would be applied to patients with a medium risk of readmission. In addition to the previous measures, the following would be incorporated:

-Schedule at least three follow-up appointments: one (via telephone) with a psychiatrist from the MHHU within 24 hours post-discharge, and two at the Community Mental Health Unit: the first within 7 days and the second between days 21 and 30.

-If the patient presents social impairment, schedule an appointment with a social worker from the Community Mental Health Unit within 14 days post-discharge.

-If the patient has a Severe Mental Disorder, schedule a nursing visit during their stay at the MHHU.

3. Intensive measures

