3.1 Intensive case management measures

The following measures would be applied to patients with a high risk of readmission or who have experienced early readmission. In addition to the measures from the previous levels, the following would be incorporated:

-Schedule at least three follow-up appointments: one, in this case, in-person, with a psychiatrist from the MHHU within 24 hours post-discharge, and two at the Community Mental Health Unit: the first within 7 days and the second between days 21 and 30.

-If the patient has a Severe Mental Disorder, schedule two nursing visits: one during the hospitalization and one in the first week post-discharge. The latter will preferably be conducted at the patient's home.

-If the patient has documented medication non-adherence, consider depot medication based on clinical characteristics.

-All readmissions and patients at high risk of readmission will be assigned a case management figure who will develop a follow-up program for each patient and manage all their appointments during the first month post-discharge. This includes reminding patients of appointments 24 hours in advance, reengaging patients in case of non-attendance, and coordinating with reference facilities.

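### The adjusted outcome model takes in every variable used in the risk scale, and no rule keeps out candidates settled after admission, one of which, physician coordination, is itself a programme measure

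*Combined protocol and SAP*

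**What the plan says.** The Data analysis section plans univariate and multivariate mixed logistic regression for the comparison with the control groups, "introducing potential confounding variables (unit occupancy, age, sex, and the variables used in the scale for estimating the risk of early rehospitalization". It sets no limit on when those variables must have been determined. The same section selects the scale's factors by univariate logistic regression and then forward stepwise selection on statistical significance.

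The candidates are listed under Construction of the Early Readmission Risk Scale. They include "discharge measures (coordination with referring physician in the CMHU and prescription of depot medication" and "admission characteristics (urgent or scheduled access route and length of stay".

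The same part of the protocol fixes when the scale is scored: "This scale will be completed by the referring physician during the initial assessment interview upon admission".

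The first general measure, for low-risk patients, is "Ensure coordination between physicians during admission and a follow-up appointment within 7 days". The reinforced level builds on it ("In addition to the previous measures, the following would be incorporated"), and so does the intensive level ("In addition to the measures from the previous levels, the following would be incorporated"). The intensive level also has a depot item: "If the patient has documented medication non-adherence, consider depot medication based on clinical characteristics". Controls continue with usual treatment.

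**The concern.** The general aim is the effect of the multicomponent programme as a whole on early readmission. Adjusting for something the programme changes takes that pathway out of the estimate. What remains is the effect of the other components, although it would be reported as the effect of the programme.

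Coordination with the community physician is the direct case, because one item can be a scale candidate, a programme measure at all three risk levels and a covariate in the outcome model. The scale is built on episodes from before the programme, when coordination could vary and predict readmission. The programme then sets out to ensure it in the experimental group.

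The other two items are weaker. Depot treatment is only to be considered, at one level and for one kind of patient. Length of stay is not a programme component, but it is known only at discharge. Both may also reflect severity or local practice.

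The direction of the error is not fixed. If the item protects against readmission, adjustment moves the estimate toward no effect. If it marks sicker patients, adjustment moves the estimate away from no effect.

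**Working it through.** The plan gives no figure for this point, so the check has three parts: the text, the possible effect on the estimate, and the chance that coordination is selected.

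**Text, item by item**

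| Candidate | When settled | Part of the programme? | Barred from scale or model? |
|---|---|---|---|
| Coordination with community physician | During admission or at discharge | Yes, every risk level | No |
| Depot prescription | At discharge | Only to be considered, intensive level | No |
| Length of stay | At discharge | No | No |

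**Effect on the estimate (coordination only)**

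From the documents: 30-day readmission risk 15.08% (Setting, 2022), used as the control risk. Assumed: coordination frequency in controls (pc) and in the programme group (pt), odds ratio of coordination for readmission (ORm), and odds ratio of the rest of the programme (ORd). It is also assumed that no unmeasured factor drives both coordination and readmission.

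Model: logit(risk) = a + ln(ORm) × coordination + ln(ORd) × programme, with a chosen so that the control risk is 15.08%. The total odds ratio compares the marginal risks; the adjusted odds ratio is ORd. Share removed = 1 − ln(ORd) / ln(total OR).

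Central case: pc 40%, pt 90%, ORm 0.6, ORd 0.8.
- Control risk is 17.57% without coordination and 11.34% with it: 0.6 × 17.57 + 0.4 × 11.34 = 15.08%.
- Programme risk is 14.57% without and 9.28% with: 0.1 × 14.57 + 0.9 × 9.28 = 9.8%.
- Total OR = (0.0981/0.9019) / (0.1508/0.8492) = 0.613; adjusted OR = 0.80.
- Share removed = 1 − 0.2231/0.4899 = 54%.

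| pc to pt | ORm | ORd (= adjusted OR) | Total OR | Share of log OR removed |
|---|---|---|---|---|
| 40% to 90% | 0.6 | 0.8 | 0.61 | 54% |
| 40% to 70% | 0.6 | 0.8 | 0.69 | 41% |
| 40% to 60% | 0.6 | 0.8 | 0.72 | 31% |
| 40% to 50% | 0.6 | 0.8 | 0.76 | 18% |
| 40% to 40% | 0.6 | 0.8 | 0.801 | essentially none |
| 50% to 80% | 0.7 | 0.8 | 0.72 | 33% |
| 60% to 90% | 0.8 | 0.6 | 0.56 | 12% |
| 40% to 90% | 0.6 | 1.0 | 0.77 | 100% |
| 40% to 90% | 1.3 | 0.8 | 0.91 | opposite direction: adjusted effect too strong |

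A second set of assumptions (pc 30% to 70%, pt 95%, ORm 0.5 to 0.9, ORd 0.8) removes 11% to 68%. One of those cases (50% to 95%, ORm 0.5) was also simulated with 400,000 episodes. The unadjusted and adjusted odds ratios were 0.566 and 0.803, against 0.568 and 0.80 by formula.

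**Chance that coordination is statistically significant**

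From the documents: 838 admissions × 15.08% gives about 126 cases at most, with an equal number of controls. Assumed: coordination in 40% of all episodes and a two-sided Wald test at 0.05, since the plan gives no entry level. With 20,000 simulations per value:

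| True OR of coordination | 0.8 | 0.7 | 0.6 | 0.5 | 1.3 |
|---|---|---|---|---|---|
| Significant | 14% | 27% | 48% | 73% | 18% |

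At an entry level of 0.10, the figure for OR 0.6 is 61%. These are single-variable tests that ignore correlation with other candidates. Nothing was computed for depot prescription or length of stay.

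**The case against.** The strongest reply is that a scale scored at the admission interview cannot contain coordination, discharge prescriptions or length of stay. They would then not be variables used in the scale and would never reach the outcome model. Their place on the candidate list could serve the separate aim of identifying risk factors. The plan also calls its covariates confounders, and a programme component is not one. This is a reasonable guess at what may happen, but it remains an inference. The list is introduced as input to building the instrument, the final selection rests on significance alone, and nothing bars the three items.

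The harm is also conditional. The item must pass selection, remain in a scale scored at admission, be shifted by the programme and affect readmission. The selection percentages address only the first step. They use the maximum number of cases, although records must be complete; with 100 cases the figure for OR 0.6 falls to about 40%. The shift could also be small. Parts of the protocol can be read as both groups being admitted to the same unit and split by home area, so shared ward staff could make coordination similar. All of this stands and limits what can be said about size.

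Finally, depot use and length of stay may carry severity information that a non-randomised comparison needs. That stands as a cost of leaving them out. The planned univariate model would show a gap between the two estimates, but it is itself confounded and cannot replace a properly adjusted model.

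**Conclusion.** The concern holds and should be fixed, with medium confidence because it depends on which items are retained. Followed as written, the plan can adjust the effectiveness estimate for a component of the programme. The problem is clear for coordination and weaker for depot prescription and length of stay.

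The documents do not give its size. Under the assumed inputs with a protective coordination effect and a real shift, the loss runs from 11% to 68% of the log odds ratio, and is total if coordination is the only active component. It is essentially nil without a shift, and the error reverses if coordination marks sicker patients. Selection of coordination is uncertain but not remote. Only the 15.08% risk and the 838 admissions are documented; every other input is an assumption.

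**What to change.** Add to Data analysis, before outcome data are examined:

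> The primary adjusted mixed logistic model uses only variables determined at or before admission: age, sex, unit occupancy at admission, and scale items known at the admission interview. Coordination with the community mental health physician, depot prescription at discharge and length of stay are not in this model, even if they enter the scale. Models that add them are reported only as labelled sensitivity or mediation analyses.

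The scale section should also state whether items not known at the admission interview can enter the scale, since the candidate list and the time of scoring do not agree on this.

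The cost is a few sentences and no new data. The small downside is that severity or area-practice information in depot use and length of stay leaves the primary model; the sensitivity analysis would show how much that matters.
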